2.2 RATIONALE

Valacyclovir is an FDA approved medication for the acute treatment of HZ, using a dose of 1000 mg three times a day for seven days, and for prolonged suppressive treatment of HSV genital disease in immunocompetent patients, using a dose of 1000 mg daily. This study evaluates the same dose as used for suppression of HSV genital disease for patients with HZO, a purpose that has not been approved by the FDA.

This proposal has been reviewed by the FDA and approved by the IRB at the NYU School of Medicine (NYUSoM).

This is the first prospective multicenter placebo-controlled RCT of prolonged suppressive antiviral treatment for chronic HZO or HZ in immunocompetent patients.

Assessment of Most Frequently Preferred Suppressive Antiviral Regimens for HZO by Cornea Specialists

The antiviral regimen to be studied was chosen in part on the basis of a second electronic survey conducted in preparation for this trial (25). Valacyclovir 500mg bid or 1000 mg daily was preferred by 64% (108/171). Valacyclovir is a prodrug of acyclovir, which has better oral absorption and bioavailability than acyclovir. The peak plasma concentration of acyclovir after 500 mg of oral valacyclovir is 3.28 mcg/mL and after 1000 mg of valacyclovir is 5.65 mcg/mL, according to the package insert. The median inhibitory concentration of acyclovir to reduce VZV plaque counts by 50% (IC50) is approximately 3 mcg/mL (48). The IC50 of acyclovir for VZV is higher than the IC50 of acyclovir for HSV type 1, which averages 0.45-1.47 mcg/mL (compared to the peak plasma concentration of 1.21 mcg/mL after 400 mg acyclovir, the dose that was effective in HEDS APT) (49). The VZV IC50 data supports the use of valacyclovir in this study. In order to facilitate compliance by having daily dosing rather than bid dosing, 1000 mg of valacyclovir will be used, the same dose approved for suppressive treatment of genital HSV disease in immunocompetent patients. Study participants will be randomized to take two 500 mg tablets of valacyclovir once daily or two tablets of placebo, because the 1000 mg valacyclovir tablet is too large to be encapsulated, as required for this masked placebo controlled study.

2.3 POTENTIAL RISKS AND BENEFITS

2.3.1 KNOWN POTENTIAL RISKS

Risks to Study Participants Relative to Benefit to Study Participants and Others

The risk of suppressive antiviral treatment is low, and in view of the protocol measures to minimize them, the risk to study participants is low relative to the clinically important potential benefits in patients with HZO and HZ in general. If suppressive valacyclovir is effective, outcomes in HZO and PHN will be improved, benefiting afflicted study participants and society.

The blood test(s) is (are) associated with the risks and discomfort of any blood test requiring one tube, equivalent to two teaspoons of blood.

Risk of Study Drug Valacyclovir

The risk related to participation in this study relates to the risk of oral antiviral treatment with valacyclovir. Valacyclovir is approved and recommended for acute treatment of HZ, but not for chronic treatment of HZ. Previous studies of long-term suppressive treatment have been done in patients with HSV disease, using a similar dose of valacyclovir 1000 mg daily in immunocompetent patients (package insert). The most common side effects of suppressive treatment of recurrent genital HSV infections in immunocompetent adults with valacyclovir 1000 mg daily include headache (35%, compared to 34% with placebo), nausea (11%, compared to 8% with placebo), and abdominal pain (11%, compared to 6% with placebo), according to the package insert. Less common side effects include dysmenorrhea (8%, placebo 4%), depression (7%, placebo 5%), arthralgia (6%, placebo 4%), vomiting (3%, placebo 2%) and dizziness (4%, placebo1%). Rates of drug discontinuation in prior studies are not listed.

According to the package insert regarding laboratory results, hematologic abnormalities occurred in 0-0.7% in adults treated with valacyclovir 1 gram daily compared to 0.8-1.5% of adults treated with placebo. In addition, AST (SGOT) liver function test abnormalities occurred in 4.1% of adults on valacyclovir 1000 mg daily, compared to 3.0% on placebo. With regard to geriatric use, elderly patients age 65 and over are more likely to have renal or CNS adverse events and hematological and liver function problems are not mentioned. With regard to adults with liver impairment including cirrhosis, dosage modification is not recommended. Despite widespread use, there is little evidence that oral acyclovir (valacyclovir is prodrug of acyclovir) causes significant liver injury, or changes in serum liver enzyme levels (http://ivertox.nih.gov/acyclovir.htm). Suppressive valacyclovir for HSV genital disease in immunocompetent patients at the same dose of 1000 mg daily and duration of one year, or longer, as used in our study has a long established safety profile with adverse events similar to placebo in numerous studies, both before and after its approval in 1995 (50). Longterm suppressive valacyclovir was not associated with laboratory abnormalities, including creatinine levels. Headache, nausea, and diarrhea were the most common adverse events attributed to the drug. Thrombotic microangiopathy that has been reported at high doses (8000 mg/d) for prolonged periods for prophylaxis of cytomegalovirus (CMV) infection, especially in severely immunosuppressed patients, has not been reported in 3050 participants in 4 trials of valacyclovir suppression of recurrent genital HSV.

If participants in this study develop side effects, such as gastrointestinal symptoms or headache, they will be instructed to take one tablet twice daily, as the study medication may be better tolerated in divided doses. Study participants with side effects that require discontinuation of the study medicine will continue to be followed, and be included in the study on an intention-to-treat basis. The study ophthalmologist will be allowed to restart the study medication after mild or moderate side effects resolve, if the study participant agrees. If side effects recur, the dose can be reduced to one pill daily, as this lower dose has been reported in a retrospective study to be effective in reducing recurrences in HZO (1).

Valacyclovir and Renal Insufficiency

Oral antiviral medications are generally very safe and can be used in patients with impaired renal function, but their dosage needs to be adjusted. For valacyclovir, a suppressive regimen of 1000 mg daily is reduced to 500 mg daily, in study participants with creatinine clearance < 30. Study participants on dialysis or with a baseline eGFR < 45 within one month prior to enrollment will be excluded from the study. On the basis of recommendations of a geriatrician, infectious disease specialist, and nephrologist, study participants with eGFRs 45 -59 will be eligible, based on assessment of potential risk/benefit ratio. Elderly patients are at increased risk for and most negatively impacted by HZO and often have reduced eGFR. Approximately 25% of people age 70 years and older can be estimated to have eGFRs between 45 and 59 (51). Study participants with a baseline eGFR of 45-59 will have repeat eGFRs prior to the three, six, nine, 12-month study visits. If the eGFR decreases to less than 45, the eGFR will be repeated. If on repeat testing the eGFR is less than 45 the study medication will be discontinued. Study participants will be told to see their primary care doctor and have eGFR repeated monthly until it is 45 or more. The study participant will continue to be followed, but the study medication will not be restarted.

The package insert contains a warning that acute renal failure can occur in the elderly, with or without reduced renal function. Nephrotoxicity is more frequent after intravenous than oral acyclovir. Serum creatinine >1.5 of the upper limit of normal occurred in 0.2% of HZ patients on 1000 mg oral valacyclovir tid and 0% of genital HSV patients on oral valacyclovir suppression with 1000 mg daily. Dehydration contributes to nephrotoxicity.

Study participants will be provided with a participant instruction sheet, which will include directions to maintain adequate hydration to decrease the likelihood of nephrotoxicity.

In a report of a population based study conducted in Canada with over 160,000 patients age 66 years or older, patients treated with the oral dose of acyclovir and valacyclovir used for acute HZ were compared to patients treated with famciclovir, with regard to the outcome of hospitalization within 30 days for acute kidney injury, and the risk was no higher with acyclovir and valacyclovir than famciclovir, a drug not known to be associated with renal toxicity (52). In this study, acute kidney injury occurred in less than 1% of patients (0.27% of acyclovir or valacyclovir treated patients and 0.28% of famciclovir treated patients). Risk factors for acute kidney injury included higher age (patients age 85 years or older: 0.62% in acyclovir/valacyclovir group and 0.71% in famciclovir group) and chronic kidney disease (1.46% in acyclovir/valacyclovir group and 1.86% in famciclovir group). Acute kidney injury related to acyclovir/valacyclovir is associated with birefringent needle crystals on urinalysis.

Although renal toxicity is an expected complication of valacyclovir, the frequency and severity of new or worsening renal disease will be monitored to determine if it is more common than expected. Study participants with follow-up eGFRs less than 45, or who develop urinary symptoms, will be referred to their primary care doctors for evaluation, including urinalysis to detect crystals, and management.

Valacyclovir and Pregnancy

Antivirals including valacyclovir (Category B) are used during pregnancy only if the potential benefit outweighs potential risk to the fetus. Women of reproductive age will need to agree to use a recommended form of contraception during the one year of study treatment, and pregnant women will be excluded by pregnancy blood testing within one month after a menstrual cycle prior to enrollment/randomization visit. Nursing women will be excluded. Study participants who become pregnant during the study will be withdrawn from the study medication and continue to be followed.

Valacyclovir and Central Nervous System (CNS) Reactions

The package insert contains a warning that agitation, hallucinations, confusion, encephalopathy, delirium and seizures can occur in patients taking valacyclovir, and that elderly patients are more likely to have these problems. HZO can also be complicated infrequently by central nervous system (CNS) vasculopathy (stroke). Study participants who have CNS adverse events will have their study medicine discontinued, at least temporarily, and be referred for neurological evaluation and treatment. If the treating physician thinks the safety of the study participant is an issue, the 24/7 help line is available, and, if necessary, to differentiate between drug and disease related CNS disease, the medical monitor can initiate the process to unmask study medication (see Manual of Procedures, MOP). CNS complications of HZ are thought to be rare, but may be under-diagnosed, and additional information regarding their frequency may be obtained in the placebo treatment arm of the study.

Valacyclovir and Thrombotic Thrombocytopenic Purpura /Hemolytic Uremic Syndrome (TTP/HUS)

The package insert has a warning that TTP/HUS has occurred in patients with advanced HIV disease and bone marrow or renal transplant recipients on 8 grams per day of valacyclovir, a dose used for cytomegalovirus, not herpes zoster or simplex. Since immunocompromise is an exclusion criterion and the dose of valacyclovir is much lower, 1 gram per day, TTP/HUS will be considered an unanticipated and serious adverse event in this study.

Protections Against Risk

The investigational plan is specifically designed to manage and minimize risks through careful selection of study participants and suppressive antiviral treatment regimen, thorough training of study investigators and coordinators, adherence to the pre-determined time points to assess study participant clinical status, and regular clinical monitoring by study Coordinating Center (CC) personnel and the Data and Safety Monitoring Committee (DSMC). Suppressive treatment with valacyclovir 1000 mg daily of immunocompetent individuals age 18 years and older is FDA approved and recommended for herpes simplex virus (HSV) genital disease. This study evaluates the efficacy and safety of valacyclovir, at the same dose used for HSV suppression, for study participants with a different diagnosis, HZO, for which valacyclovir is approved at a higher dose, for a short duration. HZO patients are generally older than HSV patients, with approximately mean age of onset of HZO of 52 years compared to ocular HSV with a mean age onset of 37 years (2, 4, 53).

In order to minimize risks of valacyclovir in an older population of study participants, a baseline eGFR will be obtained prior to enrollment. If the eGFR is 60 or more, i.e. normal, it will not be repeated for study purposes. In order not to unfairly exclude many elderly study participants by requiring an eGFR of 60 or more, a baseline eGFR of 45 or more is an eligibility criterion. Study participants with eGFRs between 45-59 will have repeat eGFR testing every 3 months during treatment with the study drug. If the eGFR decreases to less than 45, the eGFR will be repeated. If repeat eGFR is 45 or more, the study medication will be continued, and the eGFR will be repeated prior to the next study visit. If on repeat testing the eGFR is less than 45 the study medication will be discontinued. Study participants will be told to see their primary care doctor and have eGFR test repeated monthly until it is 45 or more. The study medication will not be restarted, and the participant will continue to be followed for safety assessments.

There are no known study-related risks in addition to the use of the study medication, oral valacyclovir and blood testing.

2.3.2 KNOWN POTENTIAL BENEFITS

It is unknown whether prolonged suppressive antiviral treatment with valacyclovir reduces complications of HZO, including ocular disease and PHN, although oral antiviral medication is prescribed by approximately 30% of corneal specialists according to one study, and reported effective in significantly reducing episodes of recurrent HZO disease in another recent observational study (1, 24). If this study determines that valacyclovir is effective and safe in reducing complications of HZO, study participants randomized to receive valacyclovir may directly benefit, as well as future HZO patients treated using this evidence. If the study treatment is effective and safe in decreasing the severity, duration and frequency of PHN after HZO, this may be generalizable to HZ in other locations, and benefit many patients with PHN. If suppressive antiviral treatment is ineffective or study participants receive placebo treatment, participants will not directly benefit from participation in this research. If treatment is ineffective, its current ad hoc usage in the absence of evidence will be reduced.

3 OBJECTIVES AND PURPOSE

The objective of this double-masked, multicenter placebo controlled RCT is to evaluate whether or not prolonged suppressive oral antiviral treatment with valacyclovir 1000 mg/daily reduces complications of HZO, in immunocompetent study participants, compared to treatment with placebo and standard care without prolonged systemic antiviral treatment, thereby improving the outcomes in this common and potentially vision

and life-threatening disease. Valacyclovir, a prodrug of acyclovir, has been chosen as the antiviral agent to be used in the trial due to its superior bioavailability.

Central Hypothesis:

Prolonged suppressive oral antiviral treatment with valacyclovir 1000 mg daily, compared to placebo, will be effective in reducing complications and in improving clinical outcomes in HZO.

Primary Objective:

The primary objective is to test the hypothesis that long-term suppressive antiviral therapy can reduce complications of HZO by conducting a double-masked, placebo-controlled RCT of oral valacyclovir 1000 mg daily. Specifically, we will evaluate whether or not long term suppressive antiviral therapy compared with placebo therapy delays the time to the first occurrence of new or worsening dendriform epithelial keratitis, stromal keratitis, endothelial keratitis, and/or iritis (accompanied by prespecified changes in treatment; see MOP) by 12 months (primary endpoint) in immunocompetent study participants with HZO who have a history of one of these disease manifestations within the year prior to enrollment. The primary endpoint is measured by the time to first occurrence of any one of these specified complications associated with pre-specified treatment – see MOP.

Secondary Objectives:

The secondary objectives are:

- to evaluate the effect of treatment on the primary endpoint at 18 months (6 months after the completion of study drug treatment)
 - by comparing the rates of new or worsening dendriform epithelial keratitis, stromal keratitis,
 endothelial keratitis, and/or iritis in study participants randomized to valacyclovir versus placebo
 - by comparing time to development of the primary endpoint over the 18-month period from randomization and
 - o by comparing the occurrence of the primary endpoint during the 6-month post treatment period.
- to test the hypothesis that suppressive treatment for 12 months with oral valacyclovir 1000 mg daily reduces the incidence, severity and duration of post herpetic neuralgia (PHN) compared to placebo at 12 and 18 months in study participants with HZO.
- to test the hypotheses that vaccination against herpes zoster with the Recombinant Zoster Vaccine
 (RZV) may impact the natural history of HZO, and that suppressive antiviral treatment with
 valacyclovir 1000 mg daily compared to placebo may alter the impact of this vaccination on HZO
 activity during 12 months of study treatment.

See sections 4.2.2 for details regarding additional objectives.

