4.2.1 PRIMARY ENDPOINT

The primary endpoint is the time to first occurrence of new or worsening episode of dendriform epithelial keratitis, stromal keratitis, endothelial keratitis, and/or iritis due to HZO, requiring pre-specified changes in treatment (see MOP) during the twelve months of treatment. The primary endpoint is compared for participants randomized to study medication or placebo.

To assess the primary objectives, study participants will be monitored at each visit for new or worsening of any of the following conditions

- 1. Dendriform epithelial keratitis
- 2. Stromal keratitis
 - a. Without ulceration
 - b. With ulceration
- 3. Endothelial keratitis
- 4. Iritis

The endpoint of first occurrence of new or worsening dendriform epithelial keratitis, stromal keratitis, endothelial keratitis, and/or iritis will be determined by clinical examination requiring pre-specified changes in treatment for the same disease manifestation (see MOP for definition), as there are no validated confirmatory biomarkers or other tests. Primary endpoints will be reviewed by Clinical Event Review Committee (CERC). See MOP.

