4.2.2 SECONDARY ENDPOINTS

To assess the secondary objectives, the study participants will be monitored at each visit for the following events:

- Time to development and number of episodes of new or worsening dendriform epithelial keratitis, stromal keratitis, endothelial keratitis, and/or iritis due to HZO, requiring pre-specified changes in treatment (see MOP), during the 18 months following randomization, that includes the 6 months following cessation of treatment; and during the 6 months following the end of the 12 month treatment period.
- 2. The incidence, severity, and duration of PHN at one year of treatment, and after the 6-month post-treatment follow up.
- 3. Impact of Recombinant Zoster Vaccine (RZV) vaccination on primary endpoints during 12 months of study treatment.

- 4. Development of specific manifestations of HZO, classified as dendriform epithelial keratitis, stromal keratitis (all types), endothelial keratitis, iritis requiring pre-specified changes in treatment (see MOP), neurotrophic keratopathy with or without melting and/or microbial superinfection, episcleritis, and/or scleritis during the twelve months of treatment.
- 5. Secondary glaucoma determined by IOP and treatment required.

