7.3.7 SCHEDULE OF EVENTS TABLE

Source documents include medical records, images and all other information necessary to reconstruct and evaluate the clinical trial. Study monitors will compare data entered in electronic CRF's to information in source documents to verify the accuracy of trial data.

Please see Table 1 for Schedule of Events.

Table 1: Schedule of Events.

Procedures	Screening/consent (Visit 1)	Enrollment/Randomization (Visit 2)	3-month Follow-up (Visit 3)	6-month Follow-up (Visit 4)	9-month Follow-up (Visit 5)	12-month Follow-up (Visit 6)	15-month Follow-up (Visit 7)	18-month Follow-up (Visit 8)
Informed consent	X							
Study specific review of medical records ¹	Х	х						
Study specific review of demographics	Х							
Review of inclusion/exclusion criteria ²	Х	х						
Order pregnancy test ³	Х							
Order serum creatinine blood test for eGFR determination ⁴	X ^{4,5}							
Repeat eGFR prior to visit only if baseline eGFR = 45-59 ⁵			х	х	х	х		
Study specific history of HZO treatment		х	Х	х	х	х	х	Х
Study specific ophthalmic exam		X^6	X ⁷	X ⁷	X ⁷	X ⁸	X ⁷	X ⁷
PHN score and review of medication history for PHN		Х	Х	Х	Х	Х	Х	Х
Randomization		х						
Medication dispensed and instruction sheet provided		х	х	х	х			
Assessment of possible medical events			х	х	х	х	х	Х
Assessment of possible primary endpoints			х	х	х	Х	х	Х
Assessment of possible SAEs			Х	Х	Х	Х	Х	Х

¹ Study specific review of the participant's medical history is reviewed at the screening visit and the case report form is completed at the enrollment visit. If the study participant is ineligible, the form is not completed.

² Inclusion/exclusion criteria are reviewed at the screening visit and the case report form is completed during the enrollment visit. If the study participant is ineligible at the screening visit, the form is completed then.

³ A serum pregnancy test is required of women of child-bearing potential, who have provided written informed consent and are found to be eligible. The pregnancy test should preferably be done 2-3 days after a menstrual cycle. A urine dipstick test for pregnancy will be conducted by study staff if a study participant suspects pregnancy at the time of a study visit.

⁴ A serum creatinine blood test for eGFR determination will not be required if one has been completed in the past 30 days and the results are available for review.

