7.6 PROHIBITED MEDICATIONS, TREATMENTS, AND PROCEDURES

Until a possible primary outcome is reached open label treatment of HZO eye disease with oral valacyclovir, acyclovir, or famciclovir is prohibited for duration of the study (i.e. 18 months).

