10.2 STATISTICAL HYPOTHESES

The primary objective of this randomized controlled clinical trial is to test the hypothesis that long-term suppressive antiviral treatment for 1 year with oral valacyclovir 1000 mg daily delays the time to the first occurrence of new or worsening anterior segment ocular disease (*dendriform epithelial keratitis*, *stromal keratitis*, *endothelial keratitis*, *and/or iritis*) compared to placebo by 12 months.

The secondary objectives are (1) a) to test the hypothesis that long-term suppressive antiviral treatment for 1 year with oral valacyclovir 1000 mg daily delays the time to the first occurrence of new or worsening anterior segment ocular disease (*dendriform epithelial keratitis, stromal keratitis, endothelial keratitis, and/or iritis*) compared to placebo by 18 months; and b) to test the hypothesis that the occurrence of new or worsening disease in the 6 months post treatment period is reduced for participants treated with valacyclovir compared to placebo; and (2) to test the hypothesis that suppressive treatment for 12 months with oral valacyclovir 1000 mg daily reduces the

incidence, severity and duration of post herpetic neuralgia (PHN) compared to placebo at 12 and 18 months in patients with HZO.

To evaluate these hypotheses, the following endpoints will be evaluated:

Primary Efficacy Endpoint:

The primary endpoint is the time to first occurrence of new or worsening episode of dendriform epithelial keratitis, stromal keratitis, endothelial keratitis, and/or iritis due to HZO, accompanied by pre-specified changes in treatment for the same disease manifestation of HZO (see MOP) during the twelve months of treatment. The primary endpoint is compared for participants randomized to study medication or placebo.

To assess the primary objectives, study participants will be monitored at each visit for new or worsening any of the following conditions (see MOP for definitions):

- 1. Dendriform epithelial keratitis:
- 2. Stromal keratitis
 - a. Without ulceration
 - b. With ulceration
- 3. Endothelial keratitis
- 4. Iritis

The endpoint of first occurrence of new or worsening dendriform epithelial keratitis, stromal keratitis, endothelial keratitis, and/or iritis will be determined by clinical examination accompanied by prespecified changes in treatment (see MOP), as there are no validated confirmatory biomarkers or other tests.

Secondary Efficacy Endpoints:

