To assess the secondary objectives, the study participants will be monitored at each visit for the following:

- Time to development and number of episodes of new or worsening dendriform epithelial keratitis, stromal keratitis, endothelial keratitis, and/or iritis due to HZO, requiring pre-specified changes in treatment (see MOP), during the 18 months following randomization, that includes the 6 months following cessation of treatment; and during the 6 months following the end of the 12 month treatment period.
- 2. The incidence, severity, and duration of PHN at one year of treatment, and after the 6 month post-treatment follow up.
- 3. Impact of vaccination against zoster with RZV on outcomes.
- 4. Development of specific manifestations of HZO, classified as dendriform epithelial keratitis, stromal keratitis (all types), endothelial keratitis, iritis requiring pre-specified changes in treatment (see MOP), neurotrophic keratopathy with or without melting and/or microbial superinfection, episcleritis, and/or scleritis during the twelve months of treatment.
- 5. Secondary glaucoma as determined by IOP and treatment required.

Exploratory Efficacy Endpoints:

- 1. Changes in strength and/or frequency of prescribed topical corticosteroids at 12 and 18 months.
- 2. Occurrence of stroke
- 3. Occurrence of temporal arteritis/giant cell arteritis
- 4. Occurrence of myocardial infarction

- 5. Occurrence of new or worsening malignancy
 - a. Solid tumor (other than non-melanoma skin cancer)
 - b. Hematologic malignancy
 - c. Lymphoma.
- 6. Time to development and number of episodes of new or worsening dendriform epithelial keratitis, stromal keratitis, endothelial keratitis, and/or iritis due to HZO, with a recent substantial reduction in treatment (see MOP) during 12 months of treatment.
- 7. Impact of suppressive antiviral treatment prior to enrollment on outcomes during 12 months of study treatment.

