10.3 ANALYSIS DATASETS

All study participants who were randomized into the study will comprise the intent-to-treat population, the primary analysis population for efficacy. Study participants who received at least one dose of the assigned study drug will comprise the as-treated population, the primary analysis population for safety. Note, participants on either arm can receive off study valacyclovir or other antivirals after the primary endpoint is reached or for the occurrence of herpes simplex. During the time period that other antivirals are received, participants must be off study medication. Therefore, safety analyses will be conducted in this as-treated population until participants go off treatment at the end of the study or receive off treatment antiviral therapy for a primary endpoint or for herpes simplex. For this subset of participants who receive antiviral therapy for these reasons, additional analyses of safety for the time period following resumption of study medication will be conducted. Further supportive analyses of safety will be carried out for study participants who complete 12 months of treatment. Details provided in SAP.

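### Do sections 3, 4.2.2 and 10.2 of the protocol name conflicting outcomes for the six months after treatment, so that the comparison could wrongly suggest rebound on valacyclovir?

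*Combined protocol and SAP*

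**What the plan says.** Section 3 gives three ways of looking at the primary endpoint at 18 months. The third is "by comparing the occurrence of the primary endpoint during the 6-month post treatment period". Section 4.2.1 makes that endpoint a time to first occurrence, "requiring pre-specified changes in treatment (see MOP) during the twelve months of treatment".

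Section 10.2, secondary hypothesis 1(b), states that "the occurrence of new or worsening disease in the 6 months post treatment period is reduced for participants treated with valacyclovir compared to placebo". It then says that its hypotheses will be evaluated through a list of endpoints. Item 1 of that list begins "Time to development and number of episodes of new or worsening dendriform epithelial keratitis". It has the same text as item 1 of section 4.2.2, which requires the pre-specified treatment changes and covers the whole 18 months "and during the 6 months following the end of the 12 month treatment period".

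On who is followed and counted:

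- Section 5.4.1 keeps participants in follow-up to about 18 months whether or not they have had a primary event or stopped study medication.
- Table 1 in section 7.3.7 schedules "Assessment of possible primary endpoints" at months 15 and 18 as well as during treatment.
- Section 10.3 states: "All study participants who were randomized into the study will comprise the intent-to-treat population, the primary analysis population for efficacy".

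Section 10.4.3 leaves the methods for secondary endpoints to the SAP, whose text is not part of the material examined here.

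**The concern.** Set next to each other, the sentences seem to describe three outcomes for one six-month window: a first event (section 3), a yes/no occurrence (hypothesis 1(b)), and a time plus a count (sections 4.2.2 and 10.2, item 1). The first is impossible on the section 4.2.1 definition, and no sentence says outright whether an event in year 1 removes a participant from the later comparison.

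The choice could matter. If valacyclovir works in year 1, more valacyclovir participants reach month 12 without an event and so can still have a first one. Counting only first-ever events over all randomized participants then makes the drug look worse after stopping, even if nothing has rebounded. Restricting to participants event-free at month 12 removes that effect only if everyone is equally susceptible. Otherwise the placebo survivors are the more selected, lower-risk group. A reader could take either artefact for a harmful rebound.

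**Working it through.** **Inputs.** Section 10.5 gives 12-month failure of 30% on placebo and 21.3% on valacyclovir, about 390 per arm, hazard ratio 0.67, two-sided alpha 0.05 and 80% power. The rest is assumed: equal hazards in both arms after month 12 at the year-1 placebo level, no dropout, and gamma-distributed susceptibility with variance v from 0 to 2. The documents give no value for v.

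**The plan's own figure.** With mean failure 0.2565, z = [0.087√390 − 1.96√(2 × 0.2565 × 0.7435)] / √(0.30 × 0.70 + 0.213 × 0.787) = (1.718 − 1.210)/0.6145 = 0.826, so power is 79.6%. The hazard ratio is ln 0.787 / ln 0.70 = 0.672. Both agree with section 10.5.

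**At risk at month 12.** Event-free: 390 × 0.70 = 273 placebo and 390 × 0.787 = 307 valacyclovir. With an earlier event: 117 and 83.

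**Months 12 to 18 with v = 0.** The six-month cumulative hazard is w = −ln(0.70)/2 = 0.1783, so the six-month risk is 1 − exp(−0.1783) = 16.3% in each arm.

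- First-ever events over all randomized: 0.70 × 16.3% = 11.4% and 0.787 × 16.3% = 12.9%, about 45 and 50 events. Ratio 0.787/0.70 = 1.12.
- First events among those event-free: 16.3% in both arms, ratio 1.00.
- Any episode over all randomized: 16.3% in both arms, ratio 1.00.

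**With v > 0.** Use L(s) = (1 + vs)^(−1/v), with H_p and H_v solving L = 0.70 and 0.787, and w = H_p/2. First events over all randomized are L(H) − L(H + w); divide by L(H) for the event-free denominator. Any episode is 1 − L(w). For v = 1: H_p = 0.4286, H_v = 0.2707, w = 0.2143. First events over all are 0.700 − 0.609 = 9.1% and 0.787 − 0.673 = 11.4%; among event-free, 13.0% and 14.4%; any episode, 17.6% in both.

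| Ratio, valacyclovir to placebo | v = 0 | 0.5 | 1 | 2 |
|---|---|---|---|---|
| First event, all randomized | 1.12 | 1.18 | 1.24 | 1.37 |
| First event, event-free at month 12 | 1.00 | 1.05 | 1.11 | 1.21 |
| Any episode, all randomized | 1.00 | 1.00 | 1.00 | 1.00 |

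**Chance of a nominally significant false rebound** (nominal 2.5%; 20,000 simulated trials per setting, pooled two-proportion test), from v = 0 to v = 2: 8.7% to 27.1% for the first row, 2.4% to 13.2% for the second, and 2.4% to 2.7% for the third. Check of the first row at v = 0: 0.0142/√(2 × 0.1214 × 0.8786/390) = 0.61, and P(Z > 1.96 − 0.61) is about 9%.

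**If the treatment effect persisted in full,** six-month risk on valacyclovir would be 1 − exp(−0.1783 × 0.672) = 11.3%. First events over all randomized would give (0.787 × 11.3%)/11.4% = 0.78, and any episode 11.3/16.3 = 0.69.

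**Which row does the protocol point to?** The first row needs a rule that drops the 12-month limit of section 4.2.1 but keeps its restriction to first events. No section states that rule. The second row needs a restriction to event-free participants, which no section imposes. Section 3 uses the label loosely throughout this objective: the parent bullet speaks of the endpoint at 18 months and the second sub-bullet of its timing over 18 months, and neither is possible if the label carries a 12-month limit. Table 1 uses the label the same way at months 15 and 18. Hypothesis 1(b) is made operational by the list that follows it, which matches section 4.2.2, so those two sections agree. A count of episodes within the window does not naturally stop at the first, and sections 5.4.1 and 10.3 keep participants with an earlier event under observation and in the efficacy population.

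**The case for a change.** The best case for a change is that reading the label as an event type lifts only the 12-month limit. Section 3 itself says the primary endpoint is measured by time to first occurrence, so a first-event reading of its sub-bullet is not perverse. Item 1 of section 4.2.2 offers a time and a count without saying which one tests hypothesis 1(b). Rewording would cost little, whereas choosing among outcomes after unmasking would weaken the result. The 1.12 needs no assumption about varying susceptibility.

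Part of this stands. The literal clash between sections 3 and 4.2.1 is real, the time and the count are not ranked, and no sentence says in so many words that an earlier event leaves a participant in the comparison. But leaving two secondary measures unranked is not a contradiction, and such detail belongs in the SAP to which section 10.4.3 defers. Sections 5.4.1 and 10.3 with the episode count already point one way on who is included.

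Nor is counting any episode free of assumptions. Section 7.6 restricts open-label antivirals by the words "Until a possible primary outcome is reached open label treatment of HZO eye disease", so they may be used after an event, and more placebo participants will have had one. If every participant with an earlier event took them throughout months 12 to 18 at an assumed hazard ratio of 0.67, the ratio would be 1.03 to 1.05. If instead an earlier event multiplied later hazard by an assumed 1.5 or 2, the v = 0 model gives 17.9/18.5 = 0.97 or 19.2/20.4 = 0.94. These shifts are small and are downstream effects of treatment in a randomized comparison. They give no reason to make one measure mandatory in the protocol.

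**Conclusion.** No change to the plan follows. The sub-bullet in section 3 is a clerical slip: it uses the primary endpoint's name for the type of event. Sections 4.2.2 and 10.2 supply the operative endpoint, and sections 5.4.1, 7.3.7 and 10.3 supply the follow-up and the population, so an analyst following them reaches a sound comparison in all randomized participants.

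The distortion that would be at stake is modest at the planned rates: a ratio of 1.12, rising to 1.37 only at an assumed susceptibility variance of 2. It arises only under a rule the protocol does not state. These figures assume equal hazards after month 12 and no dropout. The matter concerns one part of one secondary objective and leaves the primary analysis and the sample size untouched. What the SAP says on this window could not be checked here; it may already settle the remaining detail.
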